#### Specific Aim 1: Experimental Plan

[figure not shown]

**FMRI Data acquisition for Aim 1:** 24 older veterans with PD and 24 veterans without PD will be scanned for approximately 1 hour inside the scanner. MR images will be acquired on a 3T Siemens Magnetom Trio TIM scanner with a 32-channel receiver array head coil. BOLD fMRI scans will be acquired with a conventional Echo Planar Imaging (EPI) sequence with Field of View (FOV) =220 IRB 60613 Motor Training in PD

Study Version 6/14/16

mm, TR/TE/FA = 2000 ms/24 ms/80°; forty-seven 3mm sagittal slices (no slice gap); 3mm x 3mm in-plane resolution, and band width of 2414 Hz/pixel; Parallel Imaging: GRAPPA factor 2, 24 phase encode reference lines. Prospective real-time motion correction  will be used with all EPI fMRI scans to minimize motion artifacts. A whole-brain 3D T1-weighted MPRAGE sequence (FOV=230 mm; TR/TI/TE/FA=2250 ms/900 ms/3 ms/9°; 0.9mm x 0.9mm x 1mm resolution) will provide anatomic detail. All scans will be acquired with parallel imaging: (GRAPPA; acceleration factor = 2; 24 (for EPI) and 36 (for MPRAGE) phase encoding reference lines). A Biopac (Goleta, CA) respiration belt and finger pulse oximeter will be used to acquire physiological waveforms time-locked to fMRI acquisition. Activation paradigm design: Participants with PD will be scanned while ON and OFF their anti-parkinsonian medication at least 12 h after their last dopaminergic medication, a functionally defined “OFF”;  thereby maximizing the ability to see a therapeutic effect. Participants will spend about 1 h total in the scanner. The scanning protocol, including time spent in the scanner, will be clearly explained to all participants, and it will be verified that every participant fully understands and is prepared for the scanning procedure. Standard operating procedures for fMRI involves checking with participants throughout to make sure they are comfortable with scanning procedures and participants are removed from the magnet at any point should they require it. The experimenter or technologist will have frequent verbal contact with the participant throughout the scanning session to assure participant comfort.

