### **Outcome Measures of Functional Performance (Aim2, Hypothesis 1):**

Measures of motor function, PD QOL and explanatory measures of executive function, procedural learning, and spatial cognition will be conducted at evaluations (pre, post and 1 month follow-up). All evaluations will be performed in the safety-monitored Movement Analysis Laboratory at the Atlanta VAMC. All outcome measures will be directly measured with an instrument or self completed by the participant, except for BBS and other scales judged by a trained rater, which will be videotaped for a blinded and qualified rater (e.g., trained physical therapy students or research assistants) not involved with the project otherwise.

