### **Plans to minimize risks during Imaging:**

No one with deep brain stimulator implants will be allowed to participate in imaging.

The risks associated with the imaging procedure are the same as those associated with conventional MRI. Specifically, movement or heating of metallic implants is a potential risk, and so subjects will be extensively screened to exclude people with metallic implants, fragments, or pacemakers. Some individuals experience claustrophobic reactions in the scanner. Subjects will be informed of this prior to the study, but because it is difficult to predict who will have such a reaction, this is not a specific exclusion criterion. During the scans themselves, any subject experiencing claustrophobia will be removed from the scanner immediately. There is no invasive component to this study; therefore, discomfort, bruising, and/or infection are not risks.

There may be additional risks associated with scanning at 3T, which we address:

Effect of the static field: The FDA has approved for routine clinical use, scanners up to 4.0 T. The system that we will be using is FDA approved. There is no conclusive evidence for irreversible or hazardous bioeffects to acute, short-term exposures of humans up to 2.0 T (Shellock and Kanal, 1996). Studies have indicated some side-effects at 4.0 T, namely unusual sensations including nausea, vertigo, and metallic taste (Schenck, 1991). However, there is no evidence that this is either irreversible or harmful. If subjects experience unusual sensations, they will be withdrawn.

Effect of the gradient field: MRI operates by rapidly changing small additional fields, called gradients. By Faraday's induction law, a changing magnetic field will induce electrical currents in any conductor. Thus, rapid cycling of the gradient field can induce peripheral nerve stimulation. However, this is not substantially different at higher magnetic fields since the gradients are separate from the main magnet. Should participants experience peripheral nerve stimulation (e.g., tingling or twitching), the principal investigator and staff will withdraw the participant from the study.

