Though all efforts will be made to recruit from the veteran population served at AVAMC, to meet recruitment goals, it may be necessary to extend recruitment to non-veterans or veterans served by the Emory healthcare system. If so, we will then obtain a list of names from the Emory electronic Medical Records (EeMR) database that includes patients with a diagnosis of idiopathic PD,

and will then send a letter from a staff neurologist at the Movement Disorder program and Emory Movement Clinic, Emory School of Medicine. A follow-up call from the PI will be placed after the letter is likely to have been received by the subject (e.g., 10+ days after sending the letter). With IRB approval, the Emory Movement clinic will include this trial in a “pocket list” of trials for persons with PD.

**Informed consent:** The Emory University IRB and the VA R&D committee will approve the consent form and all recruiting materials. After being screened on the telephone for eligibility to participate in fMRI, interested potential participants will be invited to the Atlanta VAMC Rehab R&D center. To reduce veteran burden, transportation will be provided for all subjects to and from evaluations. At the first visit, the PI will present information about the study to potential participants with an approved script. In a private room devoted to research, subjects will give informed consent after the PI provides an overview of the study's protocol, associated risks and benefits and subjects have given a verbal summary demonstrating they understand study requirements. At recruitment, study procedures for the fMRI component (Aims 1 & 2) and/or the intervention component (Aim 2) will be explained in great detail. All participants' questions will be answered. Subjects will be given a copy of the consent. Participants will not be excluded for race, ethnicity or sex and will reflect the makeup of metro Atlanta.

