MRI systems reside at the Emory Wesley Woods Center for Systems Imaging with which [name] will have access due to her academic affiliation with Emory University. The MRI unit consists of a Siemens Medical Solutions (Malvern, PA) 3.0 Tesla Trio MRI scanner, a full body scanner (60 cm bore) with Sonata gradient set (gradient amplitude of 40mT/m, maximum slew rate of 200T/m/sec, minimum gradient rise time of 200 microseconds). The system is actively shielded and is equipped with 32 RF channels and the total imaging matrix (TIM) suite. Multiple coils are available for the systems, including a 12 channel head matrix coil, 8 channel head coil, 4 channel carotid coil and a 24 channel spine coil. It runs the latest Siemens VB17 software and has a number of advanced Siemens product sequences including SWI, BLADE, Diffusion Tensor Imaging & Tractography, Auto Align feature for reproducible slice positioning based on a 3D MR brain atlas, BOLD imaging and in-line analysis suite with 3D PACE realtime motion correction and single and multi-voxel spectroscopy. Stimulus/response controls for behavioral tasks concurrent with fMRI are supported by an array of hardware specifically designed to allow investigator flexibility and precision. Visual presentation is provided by a high resolution LCD projection system (1400x1050 SXGA, 4200 lumens, 1300:1 contrast ratio) delivered from the back of the suite onto a custom fit screen mounted within the bore behind the participant's head. Audio presentation is provided by an Avotec Silent Scan 3100 that has been calibrated to maintain sound pressure levels that are dependent directly on input (flat frequency response +/- 4dB, 200-4500Hz range). A fiber-optic ergonomic bilateral button response system from Psychology Software Tools exists, as well as a control unit to support custom response shapes (joysticks, steering wheels, wands) from Current Designs. All of the hardware is connected through a single switch that signals TTL trigger pulses and allows connectivity to an investigator's laptop with any non-proprietary connections (USB, 1/8" minijack audio, VGA & DVI). A dedicated stimulus and response monitoring computer running Eprime 2.0 and Presentation stimulus programming software also exists.

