### Imaging:

No one with deep brain stimulator implants will be allowed to participate in imaging.

The risks associated with the imaging procedure are the same as those associated with conventional MRI. Specifically, movement or heating of metallic implants is a potential risk, and so subjects will be screened to exclude people with metallic implants, fragments, or pacemakers. Some individuals experience claustrophobic reactions in the scanner. Subjects will be informed of this prior to the study, but because it is difficult to predict who will have such a reaction, this is not a specific exclusion criterion. During the scans themselves, any subject experiencing claustrophobia will be removed from

the scanner immediately. There is no invasive component to this study; therefore, discomfort, bruising, and/or infection are not risks.

There may be additional risks associated with scanning at 3T, which we address:

*Effect of the static field:* The FDA has approved for routine clinical use, scanners up to 4.0 T. The system that we will be using is FDA approved. There is no conclusive evidence for irreversible or hazardous bioeffects to acute, short-term exposures of humans up to 2.0 T (Shellock and Kanal, 1996). Studies have indicated some side-effects at 4.0 T, namely unusual sensations including nausea, vertigo, and metallic taste (Schenck, 1991). However, there is no evidence that this is either irreversible or harmful. If subjects experience unusual sensations, they will be withdrawn.

*Effect of the gradient field:* MRI operates by rapidly changing small additional fields, called gradients. By Faraday's induction law, a changing magnetic field will induce electrical currents in any conductor. Thus, rapid cycling of the gradient field can induce peripheral nerve stimulation. However, this is not substantially different at higher magnetic fields since the gradients are separate from the main magnet. Should participants experience peripheral nerve stimulation (e.g., tingling or twitching), the principal investigator and staff will withdraw the participant from the study.

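### Nerve stimulation during a scan triggers withdrawal from the study, with no limit to imaging; read literally, this needlessly gives up the 1-month Berg Balance assessment and that visit's adverse-event enquiry

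*Combined protocol and SAP*

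**What the plan says.** The combined protocol and SAP gives the rule twice. Section 5, Plans to minimize risks during Imaging (effect of the gradient field), reads: "Should participants experience peripheral nerve stimulation (e.g., tingling or twitching), the principal investigator and staff will withdraw the participant from the study". Section 9, Safety Monitoring, Imaging, repeats that "the principal investigator and staff will withdraw the participant from the study". No severity threshold is attached.

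Other scanner reactions are handled differently. For unusual sensations attributed to the static field, both places say "If subjects experience unusual sensations, they will be withdrawn", without saying from what. For claustrophobia, "any subject experiencing claustrophobia will be removed from the scanner immediately". Under the Aim 1 Experimental Plan, "participants are removed from the magnet at any point should they require it".

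The BBS is the primary outcome for Aim 2, Hypothesis 1. It is measured before training, 1 week after and 1 month after (Study design and Methods, Overview), and analysed at all three times (Statistical Analysis Plan for Aim 2). Functional assessment is separate from scanning: "All evaluations will be performed in the safety-monitored Movement Analysis Laboratory at the Atlanta VAMC", whereas "MRI systems reside at the Emory Wesley Woods Center for Systems Imaging". Scans are planned before and immediately after training, and imaging is analysed at those two times only. Adverse events are asked about monthly and at each evaluation (Calendar of Adverse Events).

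**The concern.** Stopping a scan for tingling or twitching is sensible. Ending all participation is a larger step, and the text gives no reason why a gradient-induced sensation should stop balance testing in another building. The plan also makes no provision for outcome assessment or adverse-event enquiry after withdrawal.

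Two things are at stake. One is avoidable missing data on the primary outcome, in a person who may already have completed 20 lessons. The other is loss of a scheduled safety contact with the very participant who had a scanner-related symptom.

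**Working it through.** **1. Scope of each rule.**

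| Reaction | Stated action | Scope |
|---|---|---|
| Nerve stimulation | Withdrawal | The study |
| Unusual sensations | Withdrawal | Not given |
| Claustrophobia | Removal | The scanner |
| Need to stop | Removal | The magnet |

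Narrower wording was available to the authors and was used for two of the four. Nothing elsewhere limits the first, or says what the second covers.

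**2. What literal application loses, by timing.**

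- *Post-training scan.* The remaining evaluation is the 1-month visit, for which no scan or imaging analysis is planned. Once post-training scanning is complete, withdrawal prevents no further planned imaging. It loses 1 of 3 BBS time points. The Screening section has all outcome measures done ON and OFF medication, so that is 2 of 3 × 2 = 6 BBS scores, plus the enquiry at that visit. If the scan comes before the post-training BBS, that assessment is lost too; the order is not stated. If an event occurs in the first of separate ON and OFF scans, one planned scan remains, and a bar on further imaging deals with that.
- *Pre-training scan.* Participation ends. Whether this scan comes before or after randomisation is not stated. If before, nobody randomised is lost. If after, the post-training and 1-month assessments are lost (4 of 6 scores).

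**3. The plan's own power figures.** Inputs from Power Analyses for Aim 2: N = 63 (21 per group), f(V) = 0.44, power 0.80, two-sided α = 0.05, post hoc between-group d = 0.90; 25 per group recruited.

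- Interaction: λ = N·f² = 63 × 0.44² = 12.2 on 4 and 2 × (63 − 3) = 120 df gives power 0.792, which reproduces the stated 0.80. (The plan prints 114 denominator df, which fits N = 60; this does not affect the point.)
- Post hoc: noncentrality d·√(n/2) = 0.90 × √10.5 = 2.92 on 40 df gives power 81.2%; d detectable at 80% power is 0.886.

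**4. Size of the loss.** The documents give no rate of nerve stimulation, so these rates are assumptions. Expected events = rate × number scanned.

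| Assumed rate | Of 63 | Of 75 |
|---|---|---|
| 1% | 0.63 | 0.75 |
| 2% | 1.26 | 1.50 |
| 5% | 3.15 | 3.75 |

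The attrition allowance is 75 − 63 = 12, or 4 per group. Every figure is below it, although the allowance must also cover all other losses.

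**5. A deliberately harsh case.** Suppose the allowance is already used up, the ANOVA is run on complete cases (not stated), and one more person is lost from a group of 21. With 21 against 20, noncentrality is 0.90 × √(21 × 20/41) = 2.88 on 39 df. Power is 80.2% and detectable d is 0.898. The plan's stated sensitivity of d = 0.90 at 80% still holds.

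**The case against.** The best counter-argument is that the rule was never meant to reach beyond imaging. It sits under imaging headings, and the same section says there is no invasive component to the study and hence no discomfort. That fits the scan better than the trial, since the Physical risks paragraph names fatigue and muscle soreness. This stands: a narrower reading is possible, and a reader should not infer that the authors certainly intended removal from the whole trial. But the text does not say so, and staff act on the text. If the narrow meaning was intended, the fix only states it.

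Second, scanning is arguably a condition of entry. Table 4 requires willingness to be scanned from everyone, and fMRI eligibility is screened by telephone. The consent text, "study procedures for the fMRI component (Aims 1 & 2) and/or the intervention component (Aim 2) will be explained in great detail", might be taken to show that the components are separable for participants with Parkinson's disease. It is weak evidence, because the controls have imaging only, and I do not rely on it. Still, a condition of entry is not a reason to stop measuring balance after the scanning is done.

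Third, a reader might infer a threat to power. The documents do not support that: 21 per group is the number left after the attrition allowance, so subtracting these losses from 21 counts attrition twice. Nor do they support a directional bias, since the rule applies to all arms alike, or loss of the event itself, which is reportable under section 8. Finally, a first event at the post-training scan may be uncommon, because those participants have already been through the same acquisition; this is plausible inference, not something the documents show.

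**Conclusion.** The point holds as a minor one. The withdrawal wording is broader than the safety purpose requires, or at best ambiguous. If followed literally after post-training scanning, it loses the 1-month BBS and one adverse-event enquiry per affected participant, with no planned scan avoided. After a pre-training scan it ends participation, and costs a randomised person's outcome data only if randomisation has already taken place.

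The number affected is unknown and probably falls within the allowance for attrition. This conclusion rests on the wording being applied as written, on no scan being planned at 1 month, and on the assumed event rates. It is a question of data retention and safety follow-up and gives no reason to doubt the trial's power or its between-arm comparison.

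**What to change.** In both places (section 5, Plans to minimize risks during Imaging; section 9, Safety Monitoring, Imaging), replace the withdrawal instruction with:

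*The scan will be stopped at once and, if needed, no further imaging will be done. The participant remains in training (unless the investigator judges otherwise) and in all non-imaging outcome and adverse-event follow-up through the 1-month visit.*

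State also that withdrawal for unusual sensations means from the scan.

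The cost is an edit to two duplicated paragraphs, with no visits beyond those already scheduled. A few participants will have BBS data without complete scans, so the imaging and behavioural samples will differ slightly. The Dosage paragraph still excludes from analysis anyone who does not complete 20 lessons. The gain is therefore confined to events at the post-training scan and to participants who go on to complete training after an event at the pre-training scan.

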#### Potential Benefit to the Subject and Others:

Given great personal and financial costs of PD-associated movement and balance deficits, strategies are clearly needed to address these impairments. With the guidance of a partner, an individual without PD, individuals with PD may be afforded the ability to focus on key aspects of mobility- dynamic and static postural control, while expanding their motor repertoire. Participants and their caregivers may enjoy taking part in the intervention. If an intensive adapted-tango therapy improves physical function and quality of life in persons with PD, it could decrease fall risk, and reduce the associated injury and mortality. There is little information about cortical and sub-cortical changes in neural activity in those with PD that may accompany improved function resulting from

rehabilitative modalities. This study will be a first step in obtaining crucial information about brain activity during lower limb function, and plastic adaptations resulting from rehabilitative modalities in individuals with PD.

#### Importance of Knowledge to be gained:

PD affects approximately 1 million Americans, 90% of which are older than 60 years. As the US population ages, cases of PD are predicted to nearly double by 2030 (Dorsey et al., 2007). Persons with PD have a 3.2 fold greater hip fracture risk than those without (Melton et al., 2006). The cost of care for hip fractures in PD is approximately \$192 million per year in the United States alone (Melton et al., 2006). Quality of life issues are at stake. This work proposes to illuminate information about brain function that is crucial to continued progress in rehabilitative care of those with Parkinson Disease. The pilot study and hypothesis-generating experience gained from this pilot work has the potential to impact greatly care and quality of life of older persons with and without PD.

**Relevance to Health Issues:** There are extreme personal, financial and social costs associated with falls in older adults and PD in the US. However, increased physical and social activity can lengthen the span of robust function in older adults and those with PD. Results from this project will contribute to improved management of care for those with PD through enhanced knowledge about brain function during lower limb movement.

## **6. Participant Selection**

### **Recruitment and Informed consent:**

**Recruitment:** We will recruit 140 adults aged 40-85, with PD stages II-III and 24 age-matched controls. Individuals without PD (controls) will be recruited from the Atlanta VAMC RR&D CoE's registry, the VA's VINCI database, as well as at senior living communities with whom the PI has a relationship. All patient information will be stored on VA secure servers (room 3A 105) of the Atlanta VA Medical Center. Only authorized study team members will have access to this information because it will be stored on a private directory with limited access and password locked file.

We will request a partial HIPAA waiver to identify potential participants for recruitment purposes from IRB and related approvals from the local VA R&D committees. We will then obtain a list from the VA Movement Disorders clinic including patients likely to have a PD diagnosis, and send them a letter, with the director's signature informing them about the study. Drs. [name] and [name], among others, will assist. A follow-up call will be placed within two weeks of the veteran likely having received the letter. A telephone screen will determine eligibility for participating in fMRI. Also, study fliers will be posted in the medical center and a PowerPoint slide ad will be broadcast throughout the medical center closed circuit TV system, such that veteran self-referrals are possible. To aid recruitment efforts, the PI will initiate meetings with community providers to explain the research goals, and request them to send a letter describing the study to patients who may qualify and have interest. The PI and staff will also visit PD community support and educational groups to present information to potential participants. Specifically, the PI will present information about the study to potential subjects at the 10+ support groups meeting monthly, organized by the GA chapter of the American Parkinson Disease Association and other PD organizations. The PI will also draft information about the trial to be included in the APDA and other PD organizations' newsletters and informational material, as well as the Michael J Fox foxfinder website for clinical trials in PD.

Though all efforts will be made to recruit from the veteran population served at AVAMC, to meet recruitment goals, it may be necessary to extend recruitment to non-veterans or veterans served by the Emory healthcare system. If so, we will then obtain a list of names from the Emory electronic Medical Records (EeMR) database that includes patients with a diagnosis of idiopathic PD,

and will then send a letter from a staff neurologist at the Movement Disorder program and Emory Movement Clinic, Emory School of Medicine. A follow-up call from the PI will be placed after the letter is likely to have been received by the subject (e.g., 10+ days after sending the letter). With IRB approval, the Emory Movement clinic will include this trial in a “pocket list” of trials for persons with PD.

**Informed consent:** The Emory University IRB and the VA R&D committee will approve the consent form and all recruiting materials. After being screened on the telephone for eligibility to participate in fMRI, interested potential participants will be invited to the Atlanta VAMC Rehab R&D center. To reduce veteran burden, transportation will be provided for all subjects to and from evaluations. At the first visit, the PI will present information about the study to potential participants with an approved script. In a private room devoted to research, subjects will give informed consent after the PI provides an overview of the study's protocol, associated risks and benefits and subjects have given a verbal summary demonstrating they understand study requirements. At recruitment, study procedures for the fMRI component (Aims 1 & 2) and/or the intervention component (Aim 2) will be explained in great detail. All participants' questions will be answered. Subjects will be given a copy of the consent. Participants will not be excluded for race, ethnicity or sex and will reflect the makeup of metro Atlanta.

